4. BMI
5. Asthma
 - a. Never
 - b. Active⁸
 - c. Ever, not active
6. Allergic / non-allergic rhinitis:
 - a. Never
 - b. Active
 - c. Ever, not active
7. Eczema diagnosis:
 - a. Never
 - b. Active
 - c. Ever, not active
8. Nasal polyps ever
9. Charlson comorbidity index

3.3.3 Candidate predictors of total costs

1. Age
2. Sex
3. Smoking status
4. BMI
5. Blood eosinophil count
6. Most recent MRC score
7. Most recent FEV₁ % predicted, with separate category for missing
8. Baseline number of exacerbations
9. Comorbidities (Diagnostic Read code prior to index date):
 - a. Asthma ever
 - b. Allergic / non-allergic rhinitis
 - a. Never
 - b. Active⁹
 - c. Ever, not active
 - c. Eczema diagnosis

⁸ For comorbidities, ‘active’ refers to those for which a diagnosis was recorded within the baseline year and/or a prior diagnosis was accompanied by a prescription for the comorbidity within the baseline year. ‘Ever’ refers to diagnosis at any time before or during the baseline period

⁹ For comorbidities, ‘active’ refers to those for which a diagnosis was recorded within the baseline year and/or a prior diagnosis was accompanied by a prescription for the comorbidity within the baseline year. ‘Ever’ refers to diagnosis at any time before or during the baseline period

- a. Never
 - b. Active
 - c. Ever, not active
 - d. Nasal polyps ever
 - e. Chronic sinusitis diagnosis ever
 - f. Gastro-oesophageal reflux disease (GERD) ever
 - g. Diabetes Mellitus ever
 - h. Osteopenia / Osteoporosis ever
 - i. Hypertension ever
 - j. Obstructive Sleep apnoea ever
 - k. Cataract ever
 - l. Ischaemic heart disease ever
 - m. Heart failure ever
 - n. Psychiatric conditions / Anxiety/ Depression ever
 - o. Sleep disorders ever
 - p. Chronic kidney disease ever
 - q. Osteoporosis (Read code diagnosis or osteoporosis drugs [bisphosphonates, denosumab, strontium ranelate or teriparatide] ever
10. Charlson comorbidity index
11. Therapy prescribed in the baseline year (yes/no)
- a. ICS / LABA
 - b. SABA
 - c. SAMA
 - d. LAMA
 - e. Theophylline

3.4 Statistical Methods – General Aspects

Summary statistics are provided for all baseline and outcome variables, for the complete dataset and by comparison groups. For continuous variables, these include:

- Sample size (n)
- Percentage non-missing
- Mean \pm Standard Deviation for normally distributed variables
- Median and Inter-quartile Range (25th and 75th percentiles) for non-normally distributed variables

For number of events per year, the summary statistics include:

- Sample size (n)
- Count and Percentage by category (distribution): 0, 1, 2, 3 and ≥ 4

For other categorical variables, the summary statistics include:

- Sample size (n)
- Count and Percentage by category (distribution)

Characteristics are compared using the chi-squared test for categorical variables and a Student's t-test for normally distributed continuous variables or a Mann-Whitney test for non-normally distributed continuous variables.

3.4.1 Outcome analyses sub-study 1

Analyses will be performed in patients on different treatment regimens, adjusted for potential confounders (see paragraph 3.3.2) in two populations:

1. The full population of patients with COPD
2. A subpopulation of patients with "classical COPD" who had FEV₁/FVC <0.70 recorded within 5 years prior to the index date, never received an asthma diagnosis and have a smoking history

Negative binomial regression is performed to estimate RRs with 95% CI for the association between high blood eosinophil counts and the number of outcome events in the outcome period.

The primary definition of high blood eosinophil counts will be $\geq 0.45 \times 10^9/L$, based on previous work. Sensitivity analyses will be performed using ≥ 0.25 , $\geq 0.35 \times 10^9/L$ and $\geq 0.55 \times 10^9/L$ as cut-points.

Additional analyses will be performed to evaluate whether the MPR modifies the associations by including interaction terms of blood eosinophil counts and MPR into the regression model

(continuous or categorical depending on best model fit).

Analyses will be repeated in patients with good adherence, defined as $MPR \geq 80\%$.

Sensitivity analyses will be performed for the full population after exclusion of patients with any diagnostic Read code for asthma recorded ever.

Additional analyses will be performed to study whether the associations are different in never-smokers and ex-smokers in the full populations.

Confounding will be evaluated by comparing the coefficients for the effect of high eosinophil counts on the outcome event in models with and without the variable included. A change in coefficient of $\geq 5\%$ will be considered relevant.

Because there are patients with missing data on BMI and smoking habits, these variables are only kept in the model if there was relevant confounding.

In the case of relevant confounding by BMI or smoking habits, these variables are included as categorical variables with a separate category for patients with missing data. This procedure will be evaluated by comparing the coefficients for the effect estimate obtained from these models with those from a model analysing only patients with complete data available.

For the variable “age at index date” a categorical and a continuous variable (with evaluation of polynomial functions) are evaluated for best model fit and greatest confounding effect.

Final models will be arrived at following a forward-selection procedure, in which variables will be added one-by-one and were retained if the coefficient for the effect estimate (high eosinophil count) changed by $\geq 5\%$. Co-linearity will be checked by evaluating variance inflation factors (VIFs).

Comorbidities, which are univariately associated with blood eosinophil counts are evaluated for potential confounding effects separately as there are uncertainties about the underlying mechanism. These variables could be potential confounders if they are predictive of the occurrence of exacerbations through a mechanism other than the one under study. However, if they are intermediate factors on the causal pathway from high eosinophil counts to event occurrence, adjustment would be inappropriate. As these underlying mechanisms are unknown, effects of $\geq 5\%$ on the effect estimate by adjustment will be separately reported.

3.4.2 Outcome analyses sub-study 2

The crude (unadjusted) risks of re-admission to hospital for COPD are reported in a life-table (Table 1) and Kaplan-Meier curves are constructed for the total population and for patients with and without high blood eosinophil counts for the maximum follow up period of 12 months after hospital discharge. Comparisons are made with a long-rank analysis.

Cox-proportional hazard regression with the time from hospital discharge date to the first re-admission date as the survival time, is performed to estimate HRs with 95% CI for the association between high blood eosinophil counts and time to re-admission over time periods

of 28 days, 12 weeks and 12 months, adjusted for potential confounders following the procedure as described for sub-study 1.

Table 1. Example of a life-table describing the time at hospital re-admission, by blood eosinophil count

Number of patients with high blood eosinophil count					Hazard probability	Survival probability
Weeks	At risk at start	Re-admission	Censored	Death		
4						
8						
12						
26						
36						
52						
Number of patients with normal blood eosinophil count					Hazard probability	Survival probability
Weeks	At risk at start	Re-admission	Censored	Death		
4						
8						
12						
26						
36						
52						
Total population					Hazard probability	Survival probability
Weeks	At risk at start	Re-admission	Censored	Death		
4						
8						
12						
26						
36						
52						

3.4.3 Outcome analyses sub-study 3

Means of the number of events per person year of follow up with standard deviations (SD) will be reported for count variables next to distributions (number and percentage) of categorical variables describing HRU in the baseline and outcome year. HRU events recorded at the index date are included in the baseline year, except medication prescriptions for which prescriptions at the index date are included in the outcome year.

Costs will be described as means with standard deviations. Costs of 4 subgroups of patients on Triple therapy at high risk of exacerbations will be compared with overall mean costs of patients with COPD in the total population by calculation of costs ratios with 95% confidence intervals, estimated by 1000 bootstrap replicates.

Non-parametric Mann-Whitney tests are performed to test differences in average costs between different populations of patients.

3.4.4 Outcome analyses sub-study 4

Two one or two-step generalized linear models with gamma distribution and log link will be used to perform regression analysis with total all-cause and total COPD-related costs as the outcome variables.

Univariate analyses will be performed to estimate unadjusted associations for all candidate predictors of total costs (see paragraph 3.3.3 for list).

All candidate predictors will be fed into a multiple regression analysis with backwards selection of the model with the best fit, based on Akaike's information criterion (AIC). An interaction term of blood eosinophil counts and smoking status will be included in the model as potential predictor next to the main effects to evaluate relevant modification of the independent effect of blood eosinophil counts by different smoking habits.

Relative costs adjusted for other predictors will be estimated from the model for patients with and without high blood eosinophil counts.

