3. A. To estimate mean all-cause and COPD-related health care resource use (HRU) and associated costs in 4 subgroups of patients who are at risk of exacerbations (i.e. a history of ≥ 2 exacerbations or ≥ 1 exacerbation leading to hospitalisation in the past 12 months) while receiving treatment with triple therapy, where the 4 subgroups are defined by the presence or absence of high blood eosinophil counts and current smoking habits
B. to compare HRU and costs with those for the total population of patients with COPD who have blood eosinophil counts available
4. To study whether the presence of high blood eosinophil counts is associated with greater all-cause and COPD-related costs in the subsequent year and to study which other easily accessible characteristics drive future costs in patients with COPD

Methods:

Study design:

An observational historical cohort study will be performed among the UK population of patients with COPD who have blood eosinophil counts available.

Patients will be characterised in a baseline year prior to the index date (ID) and outcomes will be measured in the year after ID.

Data Sources:

Analyses for sub-study 1 (association between high eosinophil counts and COPD exacerbations) will be performed in patients from OPCR. A subpopulation of patients from CPRD with linkage to Hospital Episode Statistics (HES) available will be selected for sub-studies 2–4 (association between high blood eosinophil counts and the risk of hospital re-admission for COPD and study on HRU and costs)

Study Population:

The index date (ID) will be the most recent blood eosinophil count measurement, except for sub-study 2 for which the hospital discharge date of the most recent first hospitalization for COPD within one year after a blood eosinophil count measurement will be used as ID. Eligible patients should be ≥ 40 years old and have at least 1 year of continuous data prior to and after the respective IDs, except for sub-study 2 in which patients who die or who are lost to follow-up in the outcome year are censored. Patients eligible for sub-study 1 need to be on stable treatment during the study period.

Exposures:

Only eosinophil counts measured when there was no recent (4 weeks) exacerbation recorded are considered. The primary definition of high blood eosinophil counts will be $\geq 0.45 \times 10^9/L$, based on previous work. Sensitivity analyses will be performed using ≥ 0.25 , ≥ 0.35 and $\geq 0.55 \times 10^9/L$ as the definition.

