2.5 Study designs

2.5.1 Objective 1

The index date (ID) of objective 1 will be the most recent date of a recorded blood eosinophil count, measured at the time of stable disease, defined as no COPD exacerbation within 4 weeks prior to or at ID and no change in treatment regimen, ICS dosage and substance during the study period (Figure 1).

[figure not shown]

Figure 2. Study design objective 1

Patient's demographics and clinical characteristics will be described and potential confounders will be assessed in a baseline year prior to ID.

The association between high blood eosinophil counts (at ID) and (moderate or severe) COPD exacerbations in the subsequent year will be assessed in subgroups of patients defined by smoking status (active smoker in baseline year or not) and the following treatments in the baseline year (22):

1. Short-acting bronchodilators as required only (SABA and/or SAMA)
2. Maintenance therapy with LAMA and/or LABA
3. ICS / LABA in combination inhaler
4. Triple therapy: ICS + LABA + LAMA

The primary definition of "high eosinophil counts" will be $\geq 0.45 \times 10^9/L$, based on our previous work. Sensitivity analyses will be performed using 0.25, 0.35 and 0.55 as cut-points.

Sensitivity analyses will be performed in the subgroup of patients with COPD who have never been diagnosed with asthma, i.e., no diagnostic Read code for asthma recorded ever.

Additional analyses will be performed to evaluate whether the Medication Possession Ratio (MPR) for maintenance treatments (ICS / LAMA / LABA) modifies the associations by:

1. Including interaction terms of blood eosinophil counts and MPR into the regression model (continuous or categorical depending on best model fit) to explore whether MPR significantly modifies the association and at which values
2. Repeating analyses in patients with good adherence to ICS, using the widely used cut-point of $MPR \geq 80\%$ for therapy options 3 and 4

2.5.2 Objective 2

The ID of objective 2 will be the date of the most recent first discharge from hospital admission for COPD exacerbation occurring within one year after a blood eosinophil count measured at the time of no recent exacerbation (Figure 3). Patients will be followed after ID until re-admission or death to a maximum of one year after each index date.

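### Sub-study 2 censors deaths and reads crude re-admission risk from Kaplan-Meier and a life-table, which overstates the share of patients re-admitted, potentially materially at one year

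*Protocol*

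**What the plan says.** The handling of death has to be pieced together from several places in the Protocol.

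- **Synopsis, Study Population:** in sub-study 2, "patients who die or who are lost to follow-up in the outcome year are censored". Death and loss to follow-up are treated alike.
- **Section 2.5.2:** "Patients will be followed after ID until re-admission or death to a maximum of one year after each index date".
- **Section 2.3, criterion 5:** for objective 2, only loss to follow-up is named as a reason for censoring. Death is not mentioned.
- **Section 3.4.2, descriptive part:** the output is presented as crude risks of re-admission in a life-table, and "Kaplan-Meier curves are constructed for the total population and for patients with and without high blood eosinophil counts", up to 12 months. The groups are compared by a log-rank test (misprinted in that section).
- **Section 3.4.2, adjusted part:** "Cox-proportional hazard regression with the time from hospital discharge date to the first re-admission date as the survival time", over periods "of 28 days, 12 weeks and 12 months, adjusted for potential confounders".
- **Table 1 (life-table shell):** separate columns for re-admission, censored and death, by eosinophil group and in total. The only derived columns are a hazard probability and a survival probability.
- **Section 3.2.3:** all-cause deaths are obtained from hospital data and GP records.

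No cumulative incidence or other competing-risk estimate is named.

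**The concern.** Objective 2 asks whether patients with high counts are more likely to be re-admitted, and the synopsis makes the occurrence of re-admission within 4 weeks, 12 weeks and one year the primary outcome. These are probabilities in real patients, some of whom die first.

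Censoring a death assumes that the patient could still have been re-admitted later, at the same rate as those who remain. One minus Kaplan-Meier is then the risk in a hypothetical population in which nobody dies, and only if death and re-admission are independent. It is not the proportion of discharged patients who come back.

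Two things are at stake. The first is the absolute risk in each group and in total, which will be too high. The second is the contrast of those risks between groups: if one group has more deaths, its Kaplan-Meier risk is inflated more than the other's. Section 1.1 calls COPD mortality high, and this cohort has just left hospital after an exacerbation, so deaths within the year should be expected.

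**Working it through.** **The plan's own figure first.** Section 3.6.2, Table 3 gives 10,079 patients (9,080 normal, 999 high) for a hazard ratio of 1.3, 80% power, alpha 0.05 and a 10% re-admission risk. The synopsis puts that risk at 4 weeks. Two-sided alpha is assumed. The Freedman formula for unequal groups, with k = 999/9,080 = 0.110, is

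events = (1.96 + 0.84)² × (1 + k × 1.3)² / (k × 0.3²) ≈ 1,036.

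The risk in the high group is 1 − 0.9^1.3 = 12.8%. The mean event probability is (9,080 × 0.10 + 999 × 0.128) / 10,079 = 0.1028. So N = 1,036 / 0.1028 ≈ 10,077, against 10,079 stated. The figure reproduces. It rests on a 4-week risk, where censoring deaths hardly matters (see below), so the sample size is not affected.

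**Inputs for the risk calculation.** The documents give no mortality figure and no one-year re-admission risk after discharge. The hazards below are therefore assumptions, taken as constant and shown as a range: re-admission h = 0.5 or 0.8 per year, death d = 0.1 to 0.4 per year.

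**Formulas**, with T in years:

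- Deaths censored: 1 − KM = 1 − exp(−hT)
- Proportion actually re-admitted: CIF = h/(h + d) × [1 − exp(−(h + d)T)]

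**Worked case at one year**, h = 0.5 and d = 0.4: 1 − KM = 1 − exp(−0.5) = 39.3%. CIF = (0.5/0.9) × [1 − exp(−0.9)] = 33.0%. The excess is 6.4 points before rounding.

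**Results at one year**

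| h | d | 1 − KM | CIF | Excess (points) |
|---|---|---|---|---|
| 0.5 | 0.1 | 39.3% | 37.6% | 1.7 |
| 0.5 | 0.2 | 39.3% | 36.0% | 3.4 |
| 0.5 | 0.3 | 39.3% | 34.4% | 4.9 |
| 0.5 | 0.4 | 39.3% | 33.0% | 6.4 |
| 0.8 | 0.1 | 55.1% | 52.7% | 2.3 |
| 0.8 | 0.4 | 55.1% | 46.6% | 8.5 |

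**Earlier horizons, same hazards.** At 12 weeks (T = 12/52) the excess runs from 0.1 points (h = 0.5, d = 0.1) to 0.7 points (h = 0.8, d = 0.4: 16.9% against 16.1%). At 4 weeks it is at most 0.1 points.

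A second set of assumptions starts from the plan's 10% risk at 4 weeks, with one-year mortality of 5% to 40%. The 4-week cumulative incidence is then 9.98% to 9.81%, an excess of 0.02 to 0.19 points. If the 12-week Kaplan-Meier risk were as high as 30% (assumed), the excess there would be 0.2 to 1.6 points over the same mortality range.

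**Group contrast at one year.** Assume a Kaplan-Meier risk of 40% in the normal group (h = −ln 0.6 = 0.511) and a cause-specific hazard ratio of 1.3. The Kaplan-Meier risk in the high group is 1 − exp(−1.3 × 0.511) = 48.5%, and the ratio is 48.5/40 = 1.21 whatever the mortality. The cumulative-incidence ratio depends on mortality:

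| One-year mortality, normal / high | CIF normal | CIF high | Ratio |
|---|---|---|---|
| 20% / 20% | 36.2% | 44.0% | 1.22 |
| 20% / 10% | 36.2% | 46.3% | 1.28 |
| 20% / 30% | 36.2% | 41.6% | 1.15 |
| 20% / 40% | 36.2% | 39.1% | 1.08 |

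With equal mortality the contrast is almost unchanged (1.22 against 1.21). It moves materially only when mortality differs.

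**The case against.** The case for leaving the plan alone has real content.

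- **Log-rank and Cox are sound.** With deaths censored, both validly compare the rate of re-admission among patients still alive and not yet re-admitted, that is, the cause-specific hazard. A reader might infer that the hazard ratio or the test is wrong. The documents do not support that. Gray's test answers a different question, because it also responds to differences in mortality, so replacing log-rank with it would be a preference. This stands in full.
- **The emphasis is short-term.** The hypothesis in section 1.3 concerns short-term re-admission, and the sample size uses the 4-week risk, where the excess is negligible. This stands. One year is nevertheless one of the three named horizons of the primary outcome.
- **Deaths are shown.** Table 1 counts them by interval and group, so a reader could see unequal mortality and approximate the cumulative incidence. This stands in part: the column displays deaths, but does not correct the survival probability beside it. The hazard probability column is a legitimate cause-specific quantity.
- **Evidence of unequal mortality is thin.** Section 1.1 itself calls the evidence linking high counts to mortality sparse and describes it as long-term, and the title of the cited study shows a 30-year follow-up of a general population sample. A reader might infer that the eosinophil contrast is known to be distorted. It is only a possibility that the Protocol raises.
- **Costs are separate.** A reader might suppose that inflated risks feed the cost results. They do not: sub-studies 3 and 4 count resource use directly.

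**Conclusion.** The point holds for absolute risks. The Protocol fixes both the handling of death and the estimator, and together they do not give the quantity named as the outcome. The direction is certain: whenever patients die before re-admission, one minus Kaplan-Meier with deaths censored exceeds the proportion re-admitted.

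The size depends on mortality that the documents do not state. Under constant hazards of 0.5 to 0.8 (re-admission) and 0.1 to 0.4 (death) per year, it is negligible at 4 weeks, small at 12 weeks and about 2 to 8.5 points at one year. The contrast of absolute risks between eosinophil groups is materially affected only if mortality differs between them, which is not established. The hazard-based comparisons and the sample size stand. The inconsistency between criterion 5 in section 2.3 and the synopsis on who is censored is a lesser matter, but should be resolved at the same time.

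**What to change.** In section 3.4.2:

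1. Estimate the 4-week, 12-week and one-year re-admission risks, in total and by eosinophil group, as Aalen-Johansen cumulative incidence with death before re-admission as the competing event. Use these in place of one minus Kaplan-Meier and the life-table survival probability. In this estimate, censor only true loss to follow-up and the end of the observation year.
2. Keep the log-rank test and the Cox model with deaths censored, and label both as comparisons of the cause-specific hazard of re-admission.
3. Report beside them the cause-specific hazard ratio for death without re-admission, so that a reader can judge whether mortality differs by group.
4. Gray's test may be added, but need not replace log-rank.

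Also align criterion 5 in section 2.3 with the synopsis, so that the treatment of deaths is stated once and identically.

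The cost is wording, a little more analysis in standard software and slightly lower stated one-year risks. No new data are needed, since section 3.2.3 already provides for deaths.

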1.2 Rationale

Previous work conducted at OPRI found an increased risk of exacerbations with high blood eosinophil counts. However, the role of different treatment regimens in the association between blood eosinophil count and COPD exacerbations needs to be further elucidated. It is unknown whether the association is also present in the subgroup of patients with COPD who are adherent to ICS and in patients on triple therapy, to which one third of UK patients with COPD progresses in real life (2).

It is also unknown whether patients who have high blood eosinophil counts at the time of stable disease and who experience an exacerbation that requires hospitalization have an increased risk of short-term recurrence of exacerbations and re-admission to hospital.

To our knowledge there is no information available on the burden and cost of COPD in patients on triple therapy who have high blood eosinophil counts and experience frequent exacerbations.

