3.1.2 Treatment regimens

For objective 1, groups of patients using the following treatment regimens are analysed:

1. Short-acting bronchodilators as required only (SABA and/or SAMA)
2. Maintenance therapy with LAMA and/or LABA
3. ICS / LABA in combination inhaler
4. Triple therapy: ICS + LABA + LAMA

Treatment category will be assessed based on ≥ 1 prescriptions in the baseline year.

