 - b. GOLD B: FEV₁ % predicted ≥ 50 and ≤ 1 COPD exacerbation and no hospitalization for COPD in baseline year and mMRC ≥ 2
 - c. GOLD C: FEV₁ % predicted < 50 or ≥ 2 COPD exacerbations or ≥ 1 hospitalization for COPD in baseline year) and mMRC 0–1
 - d. GOLD D: FEV₁ % predicted < 50 or ≥ 2 COPD exacerbations or ≥ 1 hospitalization for COPD in baseline year) and mMRC ≥ 2
 - e. Unknown
10. ICS/LABA combinations prescribed with dosages (most recent in the baseline year)
- a. Budesonide / formeterol (Symbicort[®] / DuoResp Spiromax[®])
 - b. Fluticasone propionate / salmeterol (Seretide[®])
 - c. Beclomethasone / formeterol (Fostair[®])
 - d. Fluticasone furoate / vilanterol (Relvar Ellipta[®])
11. Cumulative doses prescribed in the baseline year (expressed as average dose per day):
- a. Average cumulative ICS dose
 - b. Average cumulative SABA dose
 - c. Average cumulative SAMA dose

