3.3.2 Potential confounders of association between high eosinophil counts and outcomes

Analyses will be adjusted for the following potential confounders:

1. Age
2. Sex
3. Smoking status

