3.5 Bias

3.5.1 Methods to Minimize Bias

Analyses will be adjusted for all potential confounders of the associations by multiple regression analysis.

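### Sub-study 2 pools all treatment regimens, and its confounder list has no therapy item, so confounding of the re-admission hazard ratio by background therapy cannot be detected

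*Protocol*

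**What the plan says.** **Sub-study 2.** Section 3.4.2 plans a Cox model for time from discharge to first re-admission, high versus normal count, over periods "of 28 days, 12 weeks and 12 months, adjusted for potential confounders following the procedure as described for sub-study 1". Section 2.5.2 describes the same comparison, with confounder adjustment and no treatment groups.

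**Confounder list.** Section 3.3.2 opens with "Analyses will be adjusted for the following potential confounders" and names age, sex, smoking status, BMI, asthma, rhinitis, eczema and nasal polyps, ending at "9. Charlson comorbidity index". It has no regimen, ICS use or ICS dose.

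**Selection procedure.** Section 3.4.1 adds variables one at a time and keeps those that change the eosinophil coefficient by at least 5%. Comorbidities that might be intermediates are reported separately.

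**Therapy in sub-study 1.** Section 3.4.1 says: "Analyses will be performed in patients on different treatment regimens, adjusted for potential confounders (see paragraph 3.3.2) in two populations". Section 3.1.2 limits the grouping: "For objective 1, groups of patients using the following treatment regimens are analysed". The stable-therapy criterion in section 2.3 is also listed under objective 1.

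**Overall claim.** Section 3.5.1 states: "Analyses will be adjusted for all potential confounders of the associations by multiple regression analysis".

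**The concern.** The list in 3.3.2 can do without a therapy item in sub-study 1, where therapy is held fixed by design. Sub-study 2 reuses the list and the selection rule, but not the design that made the list sufficient. Its cohort may run from short-acting bronchodilators only to triple therapy, and no step in the model takes account of that.

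The protocol gives reasons to regard therapy as a candidate confounder. Section 1.1 ties ICS prescribing in the guidelines to exacerbation history and airflow limitation, so regimen partly marks severity. The Summary links eosinophil counts to ICS benefit and to exacerbation risk when ICS is withdrawn. Section 3.3.3 offers baseline-year therapy to the cost model of sub-study 4. If regimen differs between the high and normal groups and is related to re-admission, the HR carries part of that difference, and the planned procedure could not reveal it.

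**Working it through.** **1. Is sub-study 2 a pooled comparison?** The sample sizes say so. Section 3.6.1 requires 1,645 patients for each therapy group in sub-study 1. Table 3 sizes sub-study 2 as one contrast: HR 1.3, 10% risk in the normal group, 9,080 normal and 999 high, 80% power, α = 0.05. The unequal-allocation Freedman formula (two-sided) reproduces it:

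- k = 999/9,080 = 0.110
- Events D = (1.960 + 0.842)² × (1 + k·HR)² / [k(1 − HR)²] ≈ 1,036
- Risk in the high group = 1 − 0.90^1.3 = 0.128; average risk ≈ 0.1028
- N = D / 0.1028 ≈ 10,077, against 10,079 stated

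Table 3 is not in dispute. It confirms a single comparison with no regimen strata.

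**2. Does the reference to sub-study 1 import the strata?** In 3.4.2 the reference qualifies the confounder adjustment. It brings in the 5% selection over the 3.3.2 list. The regimen groups and the stable-therapy rule are each tied to objective 1, and the rule cannot select a variable that it is never offered.

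**3. How large could the effect be?** The protocol gives neither therapy by eosinophil group nor a therapy effect on re-admission, so every input here is an assumption. For a binary factor (ICS use) with hazard multiplier h, the HR is multiplied by approximately

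factor = [1 + p_high(h − 1)] / [1 + p_normal(h − 1)]

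This assumes the same h in both groups and ignores correlation with other covariates. It is closest when events are few, so it suits 28 days better than 12 months. With ICS use of 60% (high) and 75% (normal), and a true HR of 1.30:

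| h | factor | HR read | factor, imbalance reversed | HR read | change in ln HR as share of ln 1.30 |
|---|---|---|---|---|---|
| 1.3 | 1.18/1.225 = 0.963 | 1.25 | 1.038 | 1.35 | 14% |
| 1.5 | 1.30/1.375 = 0.945 | 1.23 | 1.058 | 1.38 | 21% |
| 2.0 | 1.60/1.75 = 0.914 | 1.19 | 1.094 | 1.42 | 34% |

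A second set of assumptions (true HR 1, 50% of the normal group and 40% to 65% of the high group on the therapy, h from 1.2 to 2.0) gives an apparent HR between 1.40/1.50 = 0.93 and 1.65/1.50 = 1.10.

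**4. Against the protocol's own threshold.** Five per cent of ln 1.30 (0.262) is 0.013. With 75% ICS use in the normal group, an imbalance of about 5, 4 or 2 percentage points (h = 1.3, 1.5, 2.0) would reach it. A modest imbalance, if present, would count as relevant under 3.4.1.

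**5. Cost in precision.** N/(1 − R²), with an assumed R² of 0.01, 0.05 or 0.10 between therapy and high count, turns 10,079 into 10,181, 10,610 or 11,199.

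**The case against.** **Bias is not demonstrated.** This stands. Confounding needs therapy to be associated with the count, and no section reports that. The count changes described in 3.1.1 concern oral corticosteroid courses and antibiotics, not inhaled therapy. The ICS evidence in the Summary and 1.1 fits effect modification as well as confounding. A reader might infer that the HR is biased. The documents support only that such bias would go undetected.

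**The rationale speaks to sub-study 1.** Section 1.2 says that "the role of different treatment regimens in the association between blood eosinophil count and COPD exacerbations needs to be further elucidated", but this motivates objective 1. The paragraph for objective 2 raises no treatment question. The sentence shows that regimen matters to the authors, and no more.

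**Objective 2 may be prognostic.** An HR across regimens is a legitimate answer to whether patients with high counts are re-admitted more often. This stands in part, and is a reason to keep the HR adjusted for the 3.3.2 list. But the protocol chose confounder adjustment, and 3.5.1 claims that it is complete.

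**Over-adjustment.** Regimen and FEV1 may lie downstream of eosinophilic disease, and 3.4.1 warns against adjusting for intermediates. This rules out forcing either into the primary model. It does not rule out reporting both HRs, as 3.4.1 already does for comorbidities.

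**FEV1 and comparability.** A reader might infer that sub-study 2 drops FEV1, or that the gap spoils a comparison with sub-study 1. Neither is supported: sub-study 1 does not adjust for FEV1 either, and the two sub-studies differ in database, outcome and effect measure, with no numerical comparison planned.

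**Severity is partly restricted.** Every patient in sub-study 2 has been admitted with a COPD exacerbation, and baseline tables would show ICS dose ("Average cumulative ICS dose" is listed in 3.3.1). That narrows the range and makes an imbalance visible, but does not adjust for it.

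**Conclusion.** The gap is real and is fixed by the protocol's own text: a closed confounder list, regimen safeguards tied to objective 1, and a selection rule that cannot reach therapy in the pooled Cox model. The 3.5.1 statement therefore does not hold for the re-admission HR. The size and direction of any bias cannot be derived from the documents. The shift of about 4% to 9% either way rests on an assumed 60%/75% split in ICS use and an assumed hazard multiplier of 1.3 to 2.0; an HR of 1.30 reading near 1.2 needs the top of that range. The point calls for an inexpensive improvement to the analysis and does not invalidate sub-study 2.

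**What to change.** In 3.3.2 and 3.4.2, for sub-study 2:

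- Add treatment regimen, from prescriptions in the baseline year before the index admission (the four groups of 3.1.2 plus an 'other' category), as a candidate confounder under the same 5% rule.
- Report the HR with and without regimen side by side, as 3.4.1 does for possible intermediates.
- Report the HR by ICS use (yes/no) as a secondary result, since ICS may modify the association.
- Optionally, add FEV1 % predicted with a missing category (as in 3.3.3) to the side-by-side sensitivity model, not to the primary one.

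The baseline year is the practical window. The count may precede discharge by up to a year and only one year of earlier data is guaranteed, so look-back before the count itself could be very short. Some prescriptions may therefore follow the count, which is a further reason to show both HRs.

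The cost is a wording change and a few degrees of freedom in about 10,000 patients. The data are within the protocol: baseline-year prescriptions for HES-linked patients, including LAMA, are in 3.2.4, and ICS/LABA product, ICS dose and FEV1 are in 3.3.1. The downside is that the regimen-adjusted HR may be partly over-adjusted, so it should stand beside the 3.3.2-adjusted HR.
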